6.3. Secondary Efficacy Endpoints

6.3.1. Definition of the Secondary Efficacy Endpoints

The key secondary efficacy endpoints for Induction Studies are:

- The proportion of subjects achieving MCS remission at Week 10
- The proportion of subjects achieving an endoscopic subscore of 0 at Week 10
- The proportion of subjects achieving Geboes histologic remission at Week 10
- The proportion of subjects achieving MCS remission (alternative definition) at Week 10

The key secondary efficacy endpoints for Maintenance Study are:

- The proportion of subjects achieving MCS remission at Week 58
- The proportion of subjects achieving sustained EBS remission, defined as EBS remission at both Weeks 10 and 58
- The proportion of subjects achieving 6-month corticosteroid-free EBS remission at Week 58
- The proportion of subjects achieving an endoscopic subscore of 0 at Week 58
- The proportion of subjects achieving Geboes histologic remission at Week 58
- The proportion of subjects achieving MCS remission (alternative definition) at Week 58

Please refer to [Table 6-1](#) for detailed definition for all secondary efficacy endpoints for each individual study (Cohort A Induction Study, Cohort B Induction Study, and Maintenance Study).

6.3.2. Analysis Methods for Secondary Efficacy Endpoints

The same statistical method that was described under Section 6.2.3 for testing the primary efficacy endpoint will be utilized for testing the key secondary efficacy endpoints. The key secondary efficacy endpoints will be tested in the order listed in Section 3.5. The key secondary efficacy endpoints will be tested only after the primary efficacy endpoint is shown to be statistically significant at the significance level specified in Section 3.5. Each key secondary efficacy endpoint will be tested at the same significance level that is used for the primary efficacy endpoint; testing will be stopped after the first failure to reject the null hypothesis of no difference for statistical inference. If the null hypothesis testing for the primary efficacy endpoint is not rejected, the key secondary efficacy endpoint comparisons will be considered exploratory.

Bar-charts of proportions of subjects achieving each of the key secondary efficacy endpoints by treatment group with corresponding p-values will be provided.

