#### 8.5. Efficacy Analysis

##### 8.5.1. Primary Analysis

For each individual study (Cohort A Induction Study, Cohort B Induction Study, and Maintenance Study), the primary analysis will compare each filgotinib dose group to placebo on the proportion of subjects achieving EBS remission at Week 10 (Induction Studies, Cohort A and B) and at Week 58 (Maintenance Study), respectively. The Cochran-Mantel-Haenszel (CMH) approach adjusting for stratification factors will be used for hypothesis testing of the primary endpoint within each study. See Section 8.5.3 for the significant level that will be used to declare a statistical significant treatment effect for each filgotinib dose group when compared to placebo for each individual study (Cohort A Induction Study, Cohort B Induction Study, and Maintenance Study). For evaluation of EBS remission at Weeks 10 and 58, MCS score at screening will be used as baseline value.

Subjects who do not have sufficient measurements to determine efficacy endpoints will be considered failures (ie, non-responder imputation [NRI]). Sensitivity analyses will be described in the SAP.

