##### 8.5.2. Secondary Analyses

The same statistical methods used for testing the primary efficacy endpoint will be utilized for testing the key secondary endpoints in each study (Cohort A Induction Study, Cohort B Induction Study, and Maintenance Study) separately. Subjects who do not have sufficient measurements to determine the efficacy endpoints will be considered failures (ie, NRI).

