## 8.9. Sample Size

### 8.9.1. Induction Studies (Cohorts A and B)

The sample size was chosen to ensure that a clinically meaningful difference in EBS remission rate at Week 10 could be detected when comparing filgotinib to placebo within each Induction Study.

A sample size of 130 subjects in the placebo group and 260 subjects in each filgotinib dose group (n = 650 total per cohort) will provide 90% power for each filgotinib dose group comparison to placebo at a 2-sided 0.025 significance level to detect a treatment difference in EBS remission rate of 15% (25% on filgotinib and 10% on placebo).

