- Yes (dual refractory, defined as those who have failed at least 2 classes of biologic therapies [any TNF α antagonist and vedolizumab])
 - US/Korea Males
 - Subjects other than US/Korea Males
- No
 - US/Korea Males
 - Subjects other than US/Korea Males
- Corticosteroid and Immunomodulator Treatment at baseline (at re-baseline for Maintenance Study)

Concomitant use of systemically absorbed corticosteroids and/or immunomodulator at baseline/re-baseline, including: a) systemically absorbed corticosteroids only, b) immunomodulators only, c) both, and d) neither;

Prednisone equivalent dose for subjects who are on systemically absorbed corticosteroids at baseline/re-baseline (mg/day)

Prednisone equivalent dose for subjects who are on systemically absorbed corticosteroids at baseline/re-baseline (> 0 to 10 mg/day, > 10 to 20 mg/day, > 20 mg/day)

5-aminosalicylates (yes, no)

In addition, another baseline disease characteristics table for Maintenance Study using the FAS will be generated, including the above baseline characteristics except those marked as “Induction studies only” and the following additional variables:

- MCS score at re-baseline
- MCS score at re-baseline (≤ 8 , ≥ 9)
- Partial MCS score at re-baseline
- Endoscopic subscore of 3 at week 10 (yes, no)
- Fecal calprotectin at re-baseline (≤ 250 $\mu\text{g/g}$, > 250 $\mu\text{g/g}$)
- hs-CRP at re-baseline (≤ 3 mg/L , > 3 mg/L)
- EBS remission at Week 10 (yes, no)
- MCS remission at Week 10 (yes, no)
- Endoscopic subscore of 0 at Week 10 (yes, no)
- Geboes histologic remission at Week 10 (yes, no)

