Induction	Exploratory	MCS response at Week 10	An MCS reduction of ≥ 3 points and at least 30% from baseline score with an accompanying decrease in rectal bleeding subscore of ≥ 1 point or an absolute rectal bleeding subscore of 0 or 1 at Week 10
Induction	Exploratory	Endoscopic response at Week 10	An endoscopic subscore of 0 or 1 at Week 10
Maintenance	Primary	EBS remission at Week 58	An endoscopic subscore of 0 or 1*, rectal bleeding subscore of 0, and at least a 1 point decrease in stool frequency from induction baseline to achieve a subscore of 0 or 1 at Week 58
Maintenance	Key Secondary	6-month corticosteroid-free EBS remission at Week 58	EBS remission with no corticosteroid use for the indication of UC for at least 6 months prior to Week 58 among subjects who are on corticosteroid at re-baseline (baseline of maintenance study). Subjects who weaned off steroids but required re-initiation within 6 months prior to Week 58 assessment will be considered to have not met this endpoint.
Maintenance	Key Secondary	Sustained EBS remission at Week 58	EBS remission at both Week 10 and Week 58
Maintenance	Key Secondary	MCS remission at Week 58	An MCS of 2 or less and no single subscore larger than 1 at Week 58
Maintenance	Key Secondary	An endoscopic subscore of 0 at Week 58	An endoscopic subscore of 0 at Week 58
Maintenance	Key Secondary	Geboes histologic remission at Week 58	Based on the Geboes Scale (Appendix 6), all of the following must be met to be considered in Geboes histologic remission at Week 58: Grade 0 of ≤ 0.3 , Grade 1 of ≤ 1.1 , Grade 2a of $\leq 2A.3$, Grade 2b of 2B.0, Grade 3 of 3.0, Grade 4 of 4.0, and Grade 5 of 5.0.
Maintenance	Key Secondary	MCS remission (alternative definition) at Week 58	Rectal bleeding, stool frequency, and PGA subscore of 0 and an endoscopic subscore of 0 or 1; overall MCS of ≤ 1 at Week 58
Maintenance	Exploratory	6-month corticosteroid-free MCS remission at Week 58	MCS remission with no corticosteroid use for the indication of UC for at least 6 months prior to Week 58 among subjects who are on corticosteroid at re-baseline
Maintenance	Exploratory	Sustained MCS remission at Week 58	MCS remission at both Week 10 and Week 58

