6.2.3. Analysis of the Primary Efficacy Endpoint

For the individual Induction Studies (Cohort A Induction Study and Cohort B Induction Study), a stratified Cochran-Mantel-Haenszel (CMH) test will be used to compare the treatment effect between the filgotinib 200 mg group and placebo and between the filgotinib 100 mg group and placebo separately. The CMH tests will be stratified by the following factors:

- Concomitant use of oral, systemically absorbed corticosteroids at Day 1
- Concomitant use of immunomodulators at Day 1
- Exposure to biologic agent as listed in [Appendix 2](#) (≤ 1 , > 1 ; for Cohort B Induction Study only)

For the Maintenance Study, a CMH test will be used to compare the treatment effect between filgotinib 200 mg and placebo among the subjects from the Cohort A and B Induction Studies combined being treated with filgotinib 200 mg. The CMH test will be stratified by the following factors:

- Participation in Cohort A or Cohort B
- Concomitant use of oral, systemically absorbed corticosteroids at re-baseline
- Concomitant use of immunomodulators at re-baseline

Similarly, a CMH test with the same stratification factors will be used to compare the treatment effect between filgotinib 100 mg and placebo among the subjects from the Cohort A and B Induction Studies combined being treated with filgotinib 100 mg.

The stratified CMH chi-square p-value will be provided for each of the above comparison. Strata with low numbers of subjects might be aggregated for the CMH test. The 2-sided 95% confidence interval (CI) of EBS remission rate based on normal approximation method with a continuity correction will be provided for each treatment group. In addition, non-stratified risk difference estimated along with its 2-sided 95% CI using the normal approximation (ie, the Wald method) with a continuity correction for the difference in proportions will be provided. Reference Section 3.5 for the significance level that will be used to declare a statistically significant treatment effect for each filgotinib group. Stratification variables based on the eCRF data will be used for the analysis.

Bar-charts of proportions of subjects achieving EBS remission at Week 10 and Week 58 will be provided by treatment group with corresponding p-values. In addition to the primary analysis method described above, the proportion of subjects in EBS remission who had a stool frequency subscore of 0 versus 1 will be calculated and summarized.

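### Sustained EBS remission in the Maintenance Study (H5/H6) is tested without stratifying on Week 10 remission: the test is valid but gives up power

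*SAP*

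**What the plan says.** SAP 6.3.2 carries the primary method over to every key secondary endpoint: "The same statistical method that was described under Section 6.2.3 for testing the primary efficacy endpoint will be utilized". For the Maintenance Study, SAP 6.2.3 says "The CMH test will be stratified by the following factors" and lists cohort, oral systemic corticosteroid use at re-baseline and immunomodulator use at re-baseline. It allows small strata to be pooled and plans only a non-stratified risk difference. The protocol is to the same effect. In 8.5.1 the CMH "approach adjusting for stratification factors will be used for hypothesis testing of the primary endpoint within each study", and 8.5.2 adds: "The same statistical methods used for testing the primary efficacy endpoint will be utilized for testing the key secondary endpoints in each study".

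SAP Table 6-1 defines the H5/H6 endpoint as "EBS remission at both Week 10 and Week 58". SAP 3.1.2 admits to the Maintenance Full Analysis Set subjects with either EBS remission or MCS response at Week 10, so it includes Week 10 non-remitters. SAP 5.2 already derives Week 10 EBS remission as a yes/no baseline characteristic for that set. Nothing in either document uses it as a stratum.

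SAP 3.5 fixes the order for 200 mg as H1 (EBS remission), H3 (6-month corticosteroid-free EBS remission), H5 (sustained EBS remission) and then four more endpoints. The 100 mg sequence is parallel. Table 6-1 restricts H3/H4 to subjects on corticosteroids at re-baseline.

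**The concern.** A subject not in remission at Week 10 cannot achieve sustained remission, whatever treatment follows from Week 11. Such subjects are certain failures in both arms. They carry no information about maintenance treatment, yet the planned test lets the variation in Week 10 status enter its variance. The factor is known before re-randomisation and already derived, so conditioning on it is legitimate.

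What is at stake is efficiency, not bias. If H5 or H6 fails, that dose loses its formal claims on MCS remission, endoscopic subscore of 0, Geboes histologic remission and MCS remission (alternative definition), and its alpha cannot pass to the other dose.

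**Working it through.** **Inputs from the documents.** 190 filgotinib vs 95 placebo per dose comparison, 2:1, two-sided 0.025, Week 58 EBS remission 40% vs 20% (SAP 1.3; Protocol 8.9.2). Week 10 EBS remission "25% on filgotinib and 10% on placebo" (Protocol 8.9.1). Remission or response on filgotinib at Week 10: 55% (Protocol 8.9.2).

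**Not in the documents, so assumed.** The association between Week 10 and Week 58 remission (odds ratio 1 to 6, same in both arms), the share on corticosteroids at re-baseline, and the cohort and immunomodulator mix.

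**Plan's own figure.** Power = Φ[(Δ − 2.2414·SE0)/SE1], with SE0 pooled and SE1 unpooled.
- Pooled rate (76 + 19)/285 = 0.333; SE0 = √(0.2222 × 0.015789) = 0.0592; SE1 = √(0.24/190 + 0.16/95) = 0.0543.
- Power = Φ[(0.20 − 0.1328)/0.0543] = 89.2%, or 86.3% with continuity correction. The stated power of more than 85% is reproduced.

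**Share of Week 10 remitters.** p = 25/55 = 0.4545, so about 190 × 0.4545 = 86 and 95 × 0.4545 = 43 subjects. The other 54.5% cannot succeed.

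**Direction.** In a CMH test, a stratum with no events adds zero to the numerator and zero to the variance. The expected numerator is the same with or without the Week 10 stratum, because Week 10 status is independent of the re-randomised arm. With q the remitters' pooled Week 58 remission rate, the null variances are in the ratio

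pq(1 − pq) / [pq(1 − q)] = (1 − pq)/(1 − q),

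which exceeds 1 whenever p < 1 and q > 0.

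**Hand check at odds ratio 1** (no other strata).
- Planned: 18.18% vs 9.09%; SE0 = 0.0451, SE1 = 0.0407; Φ[(0.0909 − 0.1010)/0.0407] = 40%.
- Remitters only: 40% vs 20% in 86 vs 43; SE0 = 0.0879, SE1 = 0.0805; Φ[(0.200 − 0.197)/0.0805] = 52%.

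**Simulated standalone H5 power.** 285 subjects, blocks of 3 within 8 re-randomisation strata, cohort 50%, immunomodulators 25%, no prognostic effect of these factors, 8,000 runs per cell. In the table, q = (2 × filgotinib rate + placebo rate)/3.

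| Odds ratio | Remitters' Week 58 rates | q | (1−pq)/(1−q) | Planned, 8 strata | + Week 10, 16 strata | Cohort × steroid × Week 10, 8 strata |
|---|---|---|---|---|---|---|
| 1 | 40.0/20.0% | 0.333 | 1.27 | 40% | 50% | 51% |
| 2 | 49.0/26.0% | 0.413 | 1.38 | 46% | 60% | 61% |
| 3 | 54.1/29.4% | 0.459 | 1.46 | 49% | 64% | 66% |
| 4 | 57.6/31.6% | 0.489 | 1.52 | 51% | 71% | 71% |
| 6 | 62.2/34.4% | 0.529 | 1.61 | 56% | 76% | 78% |

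The gain with 16 strata is +10 to +21 points. A second simulation with other assumed shares (steroids 25%, immunomodulators 30%, 60,000 runs) gave +9.9 to +20.7. Under the null, the stratified test rejected in 2.1–2.5% of runs, against a nominal 2.5%.

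**Sensitivity of the standalone gain.** Twelve other pairs of remitter rates, with the overall rates held at 40/20%, gave about +3 to +27 points. For odds ratios 1 to 6 with no other strata, a remitter share of 25% gave 8–28 points, 35% gave 10–29 and 60% gave 9–12.

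**After gating through H1 and H3.** Only the H5 test is changed. H3 is run in steroid users at 40% vs 20% with no extra steroid-free requirement, which flatters the gate.

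| On steroids (assumed) | H3 power | Gain in formally rejecting H5 |
|---|---|---|
| 20% | about 21% | +2 to +3 points |
| 30% | about 34% | +3.5 to +4.5 points (18–25% → 22–29%) |
| 50% | about 57% | +6 to +8 points |
| 70% | about 74% | +8 to +13 points |

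If only 80% of remitters on steroids at re-baseline are steroid-free (assumed), the gain is about +2 to +3 points at 30% on steroids and +1 to +2 at 20%. If 60% are, it is about +1 to +2 and about +1. Gated on H1 alone, it is about +10 to +18.

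**The case against.** The case against acting is substantial. The planned test is valid, and protocol and SAP consistently apply one CMH method to the primary and all key secondaries, which is a conventional choice. H5/H6 are never formally tested alone. H3/H4 come first, are confined to steroid users and are often the earlier stopping point, so the realistic formal gain at 20–30% on steroids is roughly 1 to 4.5 points. Every figure for size rests on inputs the documents do not give. The remedy gives H5/H6 different strata from every other test, departs from Protocol 8.5.2 and doubles the strata. The collapsed form drops immunomodulator use, a re-randomisation factor, in favour of one that is not.

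Most of this stands and limits the importance of the point. It does not reverse it. The direction is algebraic, and no H5 scenario examined showed a loss. Standalone precision also still matters: SAP 3.5 reports nominal significance after a failed step, and SAP 6.3.2 presents p-values for each key secondary, so H5/H6 will be read whatever happens at the gate. The 16-stratum form keeps every re-randomisation factor, and SAP 6.2.3 already allows small strata to be pooled.

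**Conclusion.** The point holds as an efficiency improvement to one key secondary endpoint; the planned test is not biased. Omitting Week 10 remission inflates the null variance of H5/H6 by about 27% to 61% and costs about 10 to 20 points of standalone power for odds ratios of 1 to 6, given the 45% remitter share implied by the planning rates. The effect on formal rejection is much smaller: about 2 to 4.5 points at 20–30% on steroids, nearer 1 to 3 if some steroid users in remission are not steroid-free, and larger only if half or more are on steroids. The association, steroid share and covariate mix are assumptions, so confidence in the size is medium. Confidence in the direction is high. No gain is claimed for the primary endpoint, where the same factor would change power by only about −1 to +4 points.

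**What to change.** Before unblinding, amend SAP 6.3.2 for sustained EBS remission (H5/H6) only:

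- Add Week 10 EBS remission (yes/no) as a further CMH stratification factor.
- State the collapsing order if strata are sparse, for example immunomodulator use first, leaving cohort × steroid × Week 10 status (8 strata).
- Report a Mantel-Haenszel stratified risk difference with its confidence interval on the same strata, alongside the non-stratified difference planned in SAP 6.2.3.
- Record the departure from Protocol 8.5.1 and 8.5.2 in SAP 6.6, with the reason.

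The primary and the other key secondaries can stay as planned. The cost is a short text change using an existing variable, a documented departure from the protocol, and 16 strata for this endpoint instead of 8 (or 8 after collapsing). No extra data are needed.

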6.4. Exploratory Efficacy Endpoints

As the exploratory efficacy endpoint comparisons are not part of the gatekeeping strategy described under Section 3.5 to control the family-wise type I error, all testing described in this section will be done in an exploratory fashion.

Analysis results of biomarkers except for hs-CRP, fecal calprotectin, and fecal lactoferrin, as exploratory endpoints, will be included into a separate biomarker analysis report outside of the study CSR. Analysis of hs-CRP, fecal calprotectin and fecal lactoferrin is described in Section 9.

6.4.1. Definition of the Exploratory Efficacy Endpoints

A subset of exploratory efficacy endpoints will be described in the CSR; for the Induction Studies these include:

- Change from baseline in HRQoL scores at Week 10
- The proportion of subjects achieving novel histologic outcomes at Week 10
- The proportion of subjects achieving endoscopic response at Week 10
- The proportion of subjects achieving MCS response at Week 10
- Change from baseline in MCS at Week 10
- Change from baseline in pMCS at Week 10
- The proportion of subjects achieving EBS remission (alternative definition) at Week 10

A subset of exploratory efficacy endpoints will be described in the CSR; for the Maintenance Study these include:

- The proportion of subjects achieving sustained MCS remission, defined as MCS remission at both Weeks 10 and 58
- The proportion of subjects achieving 6-month corticosteroid-free MCS remission at Week 58
- Change from baseline in HRQoL scores at Week 58
- The proportion of subjects achieving novel histologic outcomes at Week 58
- The proportion of subjects achieving endoscopic response at Week 58
- The proportion of subjects achieving MCS response at Week 58
- Change from baseline in MCS at Week 58
- Change from baseline in pMCS at Week 58
- The proportion of subjects achieving EBS remission (alternative definition) at Week 58

Please refer to [Table 6-1](#) and [Section 6.1](#) for detailed definitions of novel histologic outcomes, EBS remission (alternative definition), endoscopic response, and MCS response at Weeks 10 and Week 58, respectively, sustained MCS remission at Week 58, and 6-month corticosteroid-free MCS remission at Week 58 for Maintenance Study.

6.4.2. Analysis of Exploratory Efficacy Endpoints

6.4.2.1. Analysis of dichotomous efficacy endpoints

A stratified CMH test will be used to compare the percentage difference of subjects between each filgotinib group and placebo group. The CMH chi-square nominal p-value will be provided. The 2-sided 95% CI based on normal approximation method will be provided for each treatment group. In addition, non-stratified risk difference estimated along with its 95% 2-sided CI with a continuity correction will be provided.

Bar-charts of proportions of subjects achieving the exploratory event type efficacy endpoints will be provided by treatment group with corresponding nominal p-values.

6.4.2.2. Analysis of MCS and pMCS exploratory endpoints

For calculation of MCS and pMCS, please refer to rules described under [Section 6.1.1](#) for MCS and pMCS with subscores.

MCS at screening will serve as induction baseline MCS. Partial MCS at Day 1 will serve as induction baseline pMCS. If pMCS at Day 1 is missing, the screening partial MCS will be used as induction baseline.

MCS at Week 10 will serve as maintenance re-baseline MCS. Partial MCS at Maintenance Day 1 will serve as Maintenance re-baseline pMCS. Re-baseline values of MCS and partial MCS will serve as Maintenance Study baseline for change from baseline calculation.

As 2 of the 3 partial MCS components (stool frequency and rectal bleeding) will be collected through the subject daily diary, partial MCS will be calculated at all visits when PGA is scheduled to be assessed.

Descriptive statistics will be used to summarize the absolute values and change from baseline values in MCS, endoscopic subscore, stool frequency subscore, rectal bleeding subscore, PGA and partial MCS by analysis visit and treatment group for Cohort A Induction Study, Cohort B Induction Study, and Maintenance Study. Shift tables of MCS subscores from baseline to Week 10 for Induction Studies and from Week 10 to Week 58 for Maintenance Study will be provided.

Difference of mean change from baseline at Week 10 for Induction Studies and difference of mean change from re-baseline at Week 58 for Maintenance study between each filgotinib dose group and placebo for partial MCS will be tested in an exploratory fashion using an analysis of covariance (ANCOVA) model adjusting for stratification factors and baseline or rebaseline value, respectively. Last Observation Carried Forward (LOCF) approach will be used to impute the missing values. Estimated means of treatment effects and estimated differences in treatment effects between each filgotinib treatment group and the placebo group will be presented with 95% CIs and nominal p-values. Difference of mean change from baseline (or re-baseline) for partial MCS at Weeks 2, 4, and 6 for Induction Studies and at Weeks 14, 20, 26, 34, 42 and 50 for Maintenance Study will be analyzed in the same fashion. The model based estimated mean change from baseline (or re-baseline) with 95% CIs will be plotted over all analysis visits by treatment group.

